**Patients with head and neck cancer treated by radiotherapy: The
impact of fixed dentures on wellbeing and oral health related
quality of life.**

Introduction

Head and neck neoplasms are defined as tumours in the upper aerodigestive tract. The tumours origin from different tissues such as the carcinomas arising from the epithelium, and sarcomas from bone, cartilage, fat, muscle, vascular, or hematopoietic tissues. Lymphomas are tumours in the lymphoid system, and melanomas arise from melanocytes, melanin-producing cells in the skin. The sites affected by the tumour are the lips, oral cavity, pharynx, larynx, and cervical oesophagus, the nose and paranasal sinuses, salivary glands, thyroid gland and parathyroid glands, and melanoma and non-melanoma skin cancers of the head and neck (1). Head and neck cancer is the fifth most common cancer worldwide with an estimated global incidence of more than 500 000 cases per year (2). Tobacco use and alcohol consumption are the most important risk factors for these cancers, while a subgroup is caused by viral infections. Patients with early-stage disease are treated by surgery or radiotherapy, whereas patients in advanced stages receive a combination of these modalities or concurrent chemotherapy and localized radiation. The five-year survival rate after treatment is around 40-50 % (3).

Patients with head and neck cancer treated by radiotherapy suffer from acute and long-term oral side effects. Oral mucositis, pain, dysphagia, and superficial opportunistic infections are common acute side effects that in most cases cease within one month after radiotherapy has been completed. However, long-term side effects like hyposalivation, impaired taste, and trismus may be life long conditions. Moreover, altered microbiological flora of the mouth, attenuated tooth enamel, and hyposalivation are risk factors for dental caries (4-6). Other hard tissue damages caused by radiotherapy are periodontitis, and more severely osteoradionecrosis of the jaws (7). The latter condition

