is caused by poor vasculated bone. Teeth with poor prognosis should be extracted before radiotherapy begins, leading to impaired occlusion including dysfunctional aesthetics and mastication. The Swedish National Board of Health and Welfare regulations compensate extracted teeth with removable dental prostheses/dentures (8). However, using removable dentures in patients with hyposalivation after radiotherapy is complicated. Removable dentures retain poorly, or chafe the oral mucosa leading to pain in function. Also, there may be problems maintaining good dental and denture hygiene leading to dental caries and periodontitis.

To date, the impact of dental occlusion on these patients' quality of life is sparsely investigated. In one study, implant-retained mandibular overdentures in patients treated for oral cancers were followed over five years (9). Overall, the survivors' oral function and patient satisfaction were high and did not change. Impaired global health and quality of life were associated with concurrent comorbidity. Malnutrition, associated with increased morbidity and mortality, in patients treated for oral/oropharyngeal cancers was shown to impair physical functioning and hence quality of life (10). In this study dental status was poorly described, although dry mouth, pain in the mouth, and problems with social contact correlated well to malnutrition and fatigue. Speech after surgery was more impaired in patients with oral cancers than with oropharyngeal cancers because of loss of anatomically important articulatory structures leading to decreased quality of life. However, there are no prospective studies supporting better speech outcome after radiotherapy alone compared with surgery (11).

Therefore, the aim of this project was to evaluate the effect and cost effectiveness of prosthodontic rehabilitation on oral health related quality of life, general wellbeing, and nutrition in patients treated by radiotherapy, with or without combination of

chemotherapy or surgery against head and neck cancer.

Methods

Design and setting

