The study will take place in four middle sized counties in the south of Sweden. The intervention will include 30 patients with head and neck cancer recruited from a Department of Maxillofacial and Oral Surgery (the City of Jönköping, Jönköping County Council), and from the Department of Orofacial Medicine (the City of Stockholm, Stockholm County Council). Another 30 patients with the same disease will be matched controls recruited from another Department of Maxillofacial and Oral Surgery (the City of Linköping, County Council of Östergötland) and from five Departments of Orofacial Medicine (the Cities of Kalmar, Oskarshamn, and Västervik, Kalmar County Council; the Cities of Ljungby, and Växjö, Kronoberg County Council). If possible but not necessary, those controls may be prosthodontically rehabilitated with temporary removable dentures. The retest described in data collection study one will include ten patients diagnosed with head and neck tumor. All patients in the retest will be residents in the County of Jönköping.

The inclusion criteria are patients with head and neck tumours considered to receive radiotherapy, with or without combination of chemotherapy or surgery, good oncological prognosis at baseline ($\leq T2$). After referral from an ENT-specialist, those patients being diagnosed with dental infections and therapy planned for dental extraction(s) will be included.

The following general exclusion criteria will be applied: any communication problems; any comorbidity with poor prognosis; poor oncological prognosis (TNM-classification $>T2$) at baseline; imminent risk of recurrence; any technical, biological, or any other reasonable obstacle of treating patients with fixed dentures; and finally patients in the matched control group financing fixed oral prosthesis themselves.

Background data like sex, age, diagnosis, TNM-classification, hyposalivation, vertical jaw mobility, dysphagia, number and sites of extracted teeth, and weight will be investigated.

Study one – quantitative approach

Instruments

SF-36v2

SF-36v2 is a well established psychometric instrument with 36 items measuring eight domains of health-related quality of life: Physical function, physical role function, bodily pain, general health, vitality, social function, emotional role function, mental health. The two comprehensive indices – physical health and mental health - can be estimated for. The instrument is translated and validated into Swedish (17-19).

EQ-5D

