Measurements and administration of the instruments after baseline follow the study protocol, appendix 13. The study protocol after completed radiotherapy states measurements at approximately 6 and 12 months respectively, or in severe cases after the prostheses have been used for one month. Those patients who receive the instruments by mail, will be requested to immediately respond to the instruments and return them to the research coordinator in attached envelopes (prepaid postage). A reminder is sent to the patient after one and two weeks if not responding. If necessary after another week, the patient will be contacted by telephone by the research coordinator. The patients weight will be recorded at the clinic, or self-reported by mail.

Data analysis

Parametric as well as non-parametric methods will be used in the statistical inference testing. Thus, for comparison between two groups the Student t-test and the Mann-Whitney U-test and between three groups or more Two-Way Analysis of Variance the Kruskal-Wallis One-Way Anova will be applied. For comparison of proportions between groups the Chi-square-test including standardized residual are to be used. For analysing changes over time the paired t-test or the Wilcoxon Signed Rank Test (for continuous variables) or the McNemar Test (for dichotomised variables) will be applied. For estimating relation between two continuous variables the Pearson test or Spearman

Rank Order Correlation will be used. For prediction, multiple and logistic regression are to be used and in order to adjust for confounding variables such as age logistic regressions also are to be used. The pre-chosen level of significance will be $p<0.05$ in all analyses.

Study two – qualitative approach

Interviews

A dental assistant experienced in methodological or subject experiences will interview the patients during approximately one hour twice. The dialogue will start with questions on general wellbeing, and then approaching oral health related quality of life. All the interviews will start with the question “How do you feel with regard to your health?”, followed by “Can you tell me more?”. Eventually the dental assistant asks, “How do you feel with regard to your mouth?” The interview will result in a detailed and exhaustive story from different point of views. All interviews will be recorded on minidiscs.

Data collection

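### The groups are formed by clinic without randomisation, yet the protocol does not commit to recording comorbidity, which it links to quality of life, so matching or adjustment for it is not assured

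*Protocol*

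**What the plan says.** **Group formation (Protocol, Participants).** "The intervention will include 30 patients with head and neck cancer", recruited in Jönköping and Stockholm. "Another 30 patients with the same disease will be matched controls", recruited in Linköping and at the Kalmar and Kronoberg departments. Treatment group follows the recruiting clinic, and there is no randomisation. The matching factors are not named.

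**Background data (Protocol, Participants).** "Background data like sex, age, diagnosis, TNM-classification, hyposalivation, vertical jaw mobility, dysphagia, number and sites of extracted teeth, and weight will be investigated". The list names nine kinds of variable; comorbidity, tobacco and alcohol are not among them.

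**Exclusions (Protocol, Participants).** One criterion is "any comorbidity with poor prognosis". Another covers technical, biological or other obstacles to treatment with fixed dentures.

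**What the protocol says about these factors (Introduction).** From an earlier five-year study of implant-retained overdentures after oral cancer: "Impaired global health and quality of life were associated with concurrent comorbidity". On the origin of the disease: "Tobacco use and alcohol consumption are the most important risk factors for these cancers".

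**Analysis (Study one, Data analysis).** On confounding, the plan says "in order to adjust for confounding variables such as age logistic regressions also are to be used". Age is the only confounder named, as an example. Multiple regression is also listed, for prediction. On the test level: "The pre-chosen level of significance will be $p<0.05$ in all analyses".

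**The concern.** When group membership is decided by clinic, comparability rests on matching and adjustment, and both can use only what has been recorded. The protocol reports that comorbidity goes with the kind of outcome it intends to compare, then leaves it out of the variables it names.

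The outcomes most exposed are the general-health instruments, SF-36v2 and EQ-5D. They measure the general wellbeing that is part of the study aim, and through SF-6D, EQ-5D and EQ-VAS they supply the QALY weights, the main outcome of Study four. If one set of clinics treats patients with more background illness, these scores can differ between groups without any effect of the dentures, and the difference would carry through to the cost-effectiveness model. A larger sample would not reduce such a bias. A later analysis plan can choose among recorded covariates, but it cannot adjust for one that was never collected.

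**Working it through.** **1. Is comorbidity committed to anywhere?** The background list does not name it. The Study one instruments are self-reported health and oral-health scales and include no comorbidity measure. The data-analysis text names only age. Appendix 13 is not in the text at hand; it is cited for measurements and administration of the instruments after baseline, whereas comorbidity is needed at baseline. The list opens with the word 'like', so it gives examples. The text therefore supports 'not committed to', and does not support 'will not be recorded'.

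**2. Do the exclusions deal with it?** In part. Comorbidity with a poor prognosis is removed, and the criterion on obstacles to fixed dentures may remove some more. Comorbidity that neither carries a poor prognosis nor prevents a fixed denture can stay in and can still lower a general-health score.

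**3. How large could the effect be?** The protocol gives no prevalence, effect size or SD and declines a power calculation, so there is no figure of its own to reproduce. The illustration uses:

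- 30 v 30 patients with complete data (Participants);
- a Student t-test on a follow-up score (Study one, Data analysis) at 5%, with two sides assumed because sidedness is not stated;
- assumed: a difference of 10 to 30 percentage points in the share of patients with relevant comorbidity;
- assumed: comorbidity shifts the score by 0.3 to 0.8 SD.

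Bias (in SD) = difference in share × effect in SD.

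Standard error = √(2/30) = 0.258 SD.

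The false-positive rate is the rejection probability of the two-sided t-test on 58 df, with non-centrality = bias / 0.258.

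| Difference in share | Effect (SD) | Bias (SD) | Bias / SE | False-positive rate |
|---|---|---|---|---|
| 0.10 | 0.3 | 0.03 | 0.12 | 5.1% |
| 0.20 | 0.5 | 0.10 | 0.39 | 6.7% |
| 0.30 | 0.8 | 0.24 | 0.93 | 15.0% |

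A normal approximation gives nearly the same rates: 5.15%, 6.7% and 15.3%.

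For scale, the difference that 30 v 30 detects with 80% power is (1.960 + 0.842) × 0.258 = 0.72 SD. The largest bias in the table is 0.24 / 0.72, or one third of that.

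**4. What does the baseline score do?** The instruments are also completed before treatment. If comorbidity shifts a score equally at baseline and at follow-up, the shift cancels in a comparison of change. In a linear model with the baseline score as covariate, it shrinks to (1 − r) × bias, where r is the within-group correlation of baseline and follow-up (equal variances assumed). The table therefore describes the unadjusted follow-up comparison. With baseline adjustment the bias from a stable shift is smaller, and what remains comes mainly from comorbidity that alters the course after treatment.

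**The case against.** The strongest reply is that the background list is open and the appendices are not at hand, so comorbidity may well be on the case report form. That stands against any claim that adjustment is impossible. A reader might infer from the list that comorbidity will go unmeasured and cannot be matched or adjusted for; the text does not support that. However, an open list binds none of the departments to collect the item, or to collect it in the same way.

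Second, baseline scores are collected and can absorb a stable group difference. This also stands, and it limits the size of the problem. It does not remove it: the data-analysis section lists paired tests of change and two-group tests separately, and does not commit to comparing change between groups or to using the baseline score as a covariate.

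Third, the exclusions may remove more comorbidity than the poor-prognosis criterion alone. This is correct, so it would be wrong to say that all other comorbidity stays in. The restriction is still partial.

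Fourth, a reader might infer that the protocol itself makes tobacco and alcohol confounders. It does not. It calls them risk factors for getting the cancer, and every patient in both groups has the cancer. A link from smoking or drinking to general-health scores is plausible, but it is the reviewer's inference.

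Fifth, the reported comorbidity link concerns global health and quality of life. In the same summary, oral function and satisfaction were high and unchanged. The point therefore applies to SF-36v2, EQ-5D and the QALY weights; the protocol shows no such link for OHIP-14, GOHAI, JFLS-8 or OAS.

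**Conclusion.** The point holds in a limited form. The groups are formed by clinic, the protocol ties comorbidity to the domain of its general-health outcomes, and it does not commit to recording it. Matching or adjustment for comorbidity is therefore not assured for SF-36v2, EQ-5D and the QALY weights. Comorbidity carries the point; tobacco is a sensible addition and alcohol an optional one.

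The size rests wholly on assumed inputs. The central case is mild: a bias of 0.10 SD and an error rate of 6.7% instead of 5%. The 15% rate needs a large imbalance and a large effect together, in a comparison that ignores baseline scores. Without the data nobody can show which case applies. The change is worth making because it is cheap and is hard to make up for after enrolment; the documents do not show that the comparison is already invalid.

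**What to change.** In the Participants section, add to the background data a named comorbidity index or count and tobacco use (current, former, never), with alcohol use optional. State that these are collected at baseline, in the same way, at every intervention and control department. If the case report form already holds them, name them in the protocol.

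In the Study one data analysis, state that:

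- the distribution of these variables is shown by group;
- the between-group comparison of the scores and QALY weights uses a linear model with group, the baseline value of the score, the comorbidity score and one current-smoking indicator.

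The cost is a few baseline items and two or three protocol sentences, with no extra visits. The statistical downside is two extra covariates with 60 patients, so the comorbidity and smoking terms should be limited to these two. The baseline score needs no new data collection.

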In this project, an interventional case-control study will be undertaken in four middle sized counties in the south of Sweden. Based on the case control sample also a methodological study will be realized in order to test the measurements' validity and reliability, but also a descriptive qualitative content analysis study will be accomplished. All these measurements – called triangulation – are done in order to strengthen the case-control study as a power calculation is not relevant to do due to the restricted eligible/consecutive sample as well as the restricted time schedule. Finally, based on all available data, a cost-effectiveness analysis will be undertaken with the use of a decision analytic model.

Intervention

Standard treatment

In order to replace extracted teeth after radiotherapy, the standard treatment is temporary removable dental prostheses/dentures (partial or complete). Depending on the teeth remaining, those may be completely tooth or tissue supported, or tissue and tooth supported. Temporary partial dentures are completely out of acrylic. Efforts are made to design a self-cleansing partial denture that preserves the remaining teeth and oral structures. The chewing forces are distributed evenly over the entire remaining teeth and soft tissues. Oral health related quality of life in healthy patients wearing removable dentures has previously been shown (12).

Fixed dentures

The special treatment is to within a year after completed radiotherapy replace removable dentures with tooth- or implant-supported dentures. The special treatment will begin six months after completed radiotherapy, or later depending on the severity of the side effects. Tooth- and implant-supported dentures are accepted modalities in patients with total or partial edentulous (13, 14). Patients with head and neck cancers usually follow the dental implant protocol valid for healthy individuals (15, 16). However, the fixture installation will be within a year after finished radiotherapy, when the jaws are still well supplied.

Participants

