EQ-5D is an instrument containing five items measuring mobility, self-care, pain, role function, and anxiety/depression. There is also one item considering change of health condition and a VAS scale for general health. This instrument is also translated and validated into Swedish (20-22).

Oral health impact profile (OHIP)

OHIP-14 is an instrument consisting of 14 items (23). It was designed to provide a comprehensive measure of the dysfunction, discomfort and disability attributed to oral conditions. Validated Swedish versions of the OHIP-14 are available (24, 25).

General oral health assessment index (GOHAI)

GOHAI is a 12-item instrument originally developed for use with older adult populations, although more recently it has been used with populations of younger adults. It measures oral functional problems and also assesses the psychosocial impacts associated with oral disease (26). A Swedish version has been validated (27).

The Jaw Functional Limitation Scale (JFLS-8)

The JFLS-8 was developed for assessing limitations in mastication, jaw mobility, and verbal and emotional expression. It is recommended for clinical and research use in patient groups with varying functional limitations of the jaw. The instrument has been tested for reliability and validity (28, 29).

The Orofacial Aesthetic Scale (OAS)

The OAS consists of seven separate aesthetic aspects of the face, teeth, lips, and mouth — devoid of psychosocial aspects. These seven items create the OAS summary score. There is also an eight item, global assessment of overall impact. A Swedish version has

been validated (28, 30, 31).

Data collection

The written consent among with the instruments will be distributed to the patients at the clinic at baseline (before any treatment), appendix 4. The completed documents will be returned to a research coordinator/dental assistant at the Department of

Maxillofacial and Oral Surgery (the City of Jönköping, Jönköping County Council).

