Convergent validity: Spearman rank order correlations (ρ), assess convergent validity between (i) OHIP summary scores and self-reported health and (ii) OHIP subscale scores and subscale scores of the SF-36 and EQ-5D.

Study four – Cost-effectiveness analysis

Background

In order for a method in health- and dental care to be considered cost-effective, it has to be a decent relation between its extra costs and effects (no exact threshold value exist in Sweden). A cost-effectiveness analysis estimates the incremental cost-effectiveness ratio (ICER) of a method in comparison with the best option (33). The outcome measure can be of any (relevant) kind, but usually it is recommended to use quality-adjusted life-years (QALYs) which also is preferred by the Swedish Dental and Pharmaceutical Benefits Agency (34). QALY combines preferences for health states (QALY-weight) with the number of years of that health state.

In order to capture the full consequences of a treatment, it is often necessary to model future costs and effects into a longer time horizon. Even though these models cannot be seen as evidence, they can provide the most accurate estimate on the long-term cost-

effectiveness and they can furthermore handle uncertainty in order to provide a decision-maker with relevant information (35).

Data collection

Costs and effects of different prosthodontic rehabilitations, fixed and removable dentures, will be compared with costs and effects of radiotherapy of patients with head and neck cancer. Data on resource use will be gathered in the intervention and translated into costs, representing their best alternative use. Productivity loss of patients unable to work will be estimated using the human capital approach. The main outcome measure in the analysis will be QALY. QALY-weights are derived indirectly from the instruments EQ-5D and SF-6D, and directly from the EQ-VAS, all of which are analysed in Study one in this project. Other outcome measures that are more directly derived from oral health related quality of life will be used too in order to examine their relevance.

Data analysis

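### In severe cases the late questionnaire is tied to one month of prosthesis use, so a severe case never fitted has no late form due and a fitted one is measured at a different time from other patients

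*Protocol*

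**What the plan says.** **Timing of the forms.** Study one, Data collection, refers to appendix 13 for the schedule and summarises it as "measurements at approximately 6 and 12 months respectively, or in severe cases after the prostheses have been used for one month". The text shown does not define a severe case. It also does not say which of the two visits the exception replaces. The late one is the sensible reading, because fixed-denture treatment does not start before six months.

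**Timing of the treatment.** Under Intervention, Fixed dentures, the protocol states: "The special treatment will begin six months after completed radiotherapy, or later depending on the severity of the side effects". It also sets an outer limit: "The special treatment is to within a year after completed radiotherapy replace removable dentures with tooth- or implant-supported dentures".

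**Groups.** Under Participants, "The intervention will include 30 patients with head and neck cancer" and "Another 30 patients with the same disease will be matched controls". A temporary removable denture is optional for controls.

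**Use of the forms.** Study one, Data analysis, lists two-sample tests between groups and paired tests over time. In Study four, Data collection, "QALY-weights are derived indirectly from the instruments EQ-5D and SF-6D, and directly from the EQ-VAS", all from the Study one instruments.

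**Interviews.** Study two, Data collection, places its two interviews at about 6 and 12 months after radiotherapy and makes no exception for prosthesis use.

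**The concern.** The late outcome should fall due on a rule that does not depend on how treatment went. For most patients it does: about 12 months after radiotherapy. For severe cases it falls due only after a prosthesis has been fitted and worn for a month. This does two things.

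- **Selection.** A severe case whose prosthesis is never fitted, for whatever reason, does not reach the trigger, so the late form is never due. These patients are likely to have had a poor course.
- **Timing.** A severe case fitted late is compared with patients measured at a different distance from radiotherapy. The comparison then mixes the effect of the denture with time since cancer treatment.

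If this happens more often in the intervention group, that group's late scores look better than the group really is. The late utility weights passed to the cost-effectiveness model carry the same tilt. Analysis cannot restore a form that was never requested, so the point belongs in the data-collection rule and cannot be left to an analysis plan.

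**Working it through.** The protocol gives no dropout rate, SD, effect size or share of severe cases, and it declines a power calculation. There is therefore no stated figure to reproduce. The check has two parts.

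**1. Which patients have a late form due, in the text shown**

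| Patient | Late form due at about 12 months? |
|---|---|
| Intervention, not severe, fitted | Yes |
| Intervention, not severe, never fitted | Yes |
| Intervention, severe, fitted late | No; after one month of use |
| Intervention, severe, never fitted | No time point stated |
| Control without a denture, not severe | Yes |
| Control without a denture, severe | Only the calendar visit can apply |
| Control with a removable denture, severe | Unclear; the exception may apply |

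The gap is the fourth row. The timing difference is the third row set against the calendar-timed rows.

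**2. How much a one-sided gap could matter (illustration)**

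Inputs:
- From the protocol: 30 per group (Participants) and significance at 0.05 (Study one, Data analysis).
- Assumed: a two-sided test (the protocol does not say), SD of 1 in both groups, no true difference, all 30 controls scored, *k* = 2 to 6 intervention patients unscored, and those patients *g* = 0.5 to 1.0 SD worse than the scored ones.

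With m = k/30, the full-group mean is (1 − m)·μ + m·(μ − g) = μ − m·g, where μ is the mean of the scored patients. The scored patients therefore overstate the group by

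bias b = m·g.

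The standard error is se = √(1/(30 − k) + 1/30). By normal approximation the chance of rejecting a true null is Φ(b/se − 1.96) + Φ(−b/se − 1.96).

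Lower end: k = 2, g = 0.5. b = 0.067 × 0.5 = 0.033 SD; se = √(1/28 + 1/30) = 0.263; rejection 5.2%.

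Upper end: k = 6, g = 1.0. b = 0.20 × 1.0 = 0.20 SD; se = √(1/24 + 1/30) = 0.274; b/se = 0.73; rejection 11.3%.

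| Unscored of 30 | Bias, error at g = 0.5 | Bias, error at g = 1.0 |
|---|---|---|
| 2 | 0.03 SD, 5.2% | 0.07 SD, 5.7% |
| 3 | 0.05 SD, 5.4% | 0.10 SD, 6.6% |
| 5 | 0.08 SD, 6.1% | 0.17 SD, 9.4% |
| 6 | 0.10 SD, 6.5% | 0.20 SD, 11.3% |

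This covers selection only. The direction of the timing effect cannot be derived from the protocol.

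**The case against.** **The strongest case against.** The default is a calendar visit, and only severe cases depart from it. Replacement is meant to take place within a year of radiotherapy, so delays may be short and few patients affected. The exception is not confined to the intervention group: a control with a removable denture could also be a severe case. Appendix 13 may define severe cases or provide a fallback visit. Non-responders to mailed forms are pursued with two reminders and a telephone call.

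**What of it stands.** The number affected may well be small, and the imbalance between groups is an inference, certain only against controls without a denture. If appendix 13 closes the gap, the main text should say so. The reminders do not help, because they pursue patients who have been sent a form, not patients whose form has not been triggered.

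**Stronger readings that the document does not support.**
- *Everyone never fitted is lost, and the late comparison rests on survivors who reached a denture.* Non-severe unfitted patients keep the 12-month form, and controls need no denture.
- *The missing rule for deaths is a defect.* No questionnaire can be completed after death, and how deaths are analysed is commonly left to the statistical analysis plan, which is not shown.
- *Utility weights from living patients are wrong.* Study four, Background, defines the QALY as a weight combined with years in the state, so survival enters separately. What remains is that late weights for delayed cases are conditional on a fitted prosthesis.
- *Mortality measures the bias.* The Introduction says "The five-year survival rate after treatment is around 40-50" per cent. With a constant hazard, one-year survival is 0.4^(1/5) = 0.833 to 0.5^(1/5) = 0.871, or 5.0 to 3.9 deaths per 30. But this is head and neck cancer in general, whereas entry here is limited to T2 or lower. Deaths also occur in both groups, and only a difference between groups in who is scored biases the comparison.

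**Conclusion.** The concern holds in a narrow form. The exception makes the late form of a severe case depend on being fitted and wearing a prosthesis for a month. As the text stands, a severe case never fitted has no late assessment, and a severe case fitted late is measured off schedule. The effect probably falls mainly on the intervention group, where later treatment is foreseen, and would then favour fixed dentures.

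The size is not known. The range of 0.03 to 0.20 SD, with a true error rate of about 5% to 11%, rests on assumed numbers of unscored patients, an assumed deficit and fully scored controls. At its lower end it is negligible. The conclusion also rests on appendix 13 containing no fallback. This is an inexpensive improvement to the measurement rule. It is not evidence that the late comparison as a whole is invalid.

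**What to change.** Amend Study one, Data collection, and appendix 13 if needed, so that:

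1. every living patient in both groups completes the instruments at about 12 months after radiotherapy, whether or not a prosthesis has been fitted;
2. this 12-month form is the one used for the between-group comparison;
3. the form after one month of prosthesis use is kept for delayed patients as an additional measurement, not a substitute.

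The change concerns only when questionnaires are sent and leaves treatment untouched. It costs a change of wording and one extra mailed form per delayed patient, and Study two already plans contact at about 12 months. The drawback is that delayed patients will be scored before they have had the benefit of the prosthesis, so the estimated benefit at 12 months may be smaller. The additional form will still show their scores once the prosthesis is in use.
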